## Protocol Summary/Submission Application

**C. Where will the children participate? (Check all that apply):**

- CW Hospital/Facility:** PICU
  - CW Outpatient Clinic/Facility:** [Click here to enter text.](#)
  - Froedtert Facility:** [Click here to enter text.](#)
  - MCW lab/office:** [Click here to enter text.](#)
  - Home**
  - School**
- If School is checked, have you obtained the necessary permission from the school district?**
- No  Yes (if YES, include documentation of permission in submission package)
- Other - Specify:** [Click here to enter text.](#)
- If Other is checked, have you obtained the necessary permission?**
- No  Yes (if YES, include documentation of permission in submission package)

**D. Are any of the children Wards (46.409) of the State or any other agency, institution, or entity?**

- No  Yes
- If YES, contact the HRPP office prior to submission and provide protocol-specific details:**

**E. Risk Levels For Studies Involving Children**

**Check the category below that best represents the degree of risk and benefit to which the children in this study will be exposed.**

*More than one category may be indicated such as when a protocol involves both an experimental and a control group. In these cases, specify which category you believe applies to which group. The IRB will consider the Principal Investigator's assessment and rationale regarding the risk level for this study but it is ultimately the IRB's responsibility to determine appropriate risk levels.*

- Risk Level 1 (46.404/50.51):** (Research not involving greater than minimal risk.) Minimal risk means that the probability and magnitude of harm or discomfort anticipated in the research are not greater in and of themselves than those ordinarily encountered in daily life or during the performance of routine physical or psychological examinations or tests.

**Provide protocol specific rationale (for each group):** [Click here to enter text.](#)

- Risk Level 2 (46.405/50.52):** (Research involving greater than minimal risk but presenting the prospect of direct benefit to the individual subjects.) More than minimal risk to children is presented by an intervention or procedure that holds out the prospect of direct benefit for the individual subject, or by a monitoring procedure that is likely to contribute to the subject's well-being.

**Provide rationale for why/how:**

- (a) **the risk is justified by the anticipated benefit to the subjects (for each group):** PENFS device use is offered as a non-medication modality to these subjects for treatment of PSH symptoms. Improvement in PSH symptoms and reduction in need for medications to treat PSH could potentially decrease the adverse effects associated with use of these medications.

## Protocol Summary/Submission Application

	
(b) the relation of the anticipated benefit to the risk is at least as favorable to the subjects as that presented by available alternative approaches (for each group): Reducing the need of neuro-sedative medications and decreasing the side effects of these medications is a benefit for these subjects in comparison to the discomfort of this device placement which is slight to minor. No significant side effects have been reported with the use of this device for other indications.

	
Risk Level 3 (46.406/50.53): (Research involving greater than minimal risk and no prospect of direct benefit to individual subjects, but likely to yield generalizable knowledge about the subject's disorder or condition.) More than minimal risk to children is presented by an intervention or procedure that does not hold out the prospect of direct benefit for the individual subject, or by a monitoring procedure which is not likely to contribute to the well-being of the subject.

Which intervention(s) or procedure(s) present more than minimal risk without offering the prospect of direct benefit to individual subjects (for each group):
 
Provide rationale for why/how:
 
(a) the risk of the intervention(s) or procedure(s) represents a minor increase over minimal risk (for each group): Click here to enter text.
 
(b) the intervention(s) or procedure(s) presents experiences to subjects that are reasonably commensurate with those inherent in their actual or expected medical, dental, psychological, social, or educational situations (for each group): Click here to enter text.
 
(c) the intervention(s) or procedure(s) is likely to yield generalizable knowledge about the subjects' disorder or condition which is of vital importance for the understanding or amelioration of the subjects' disorder or condition (for each group): Click here to enter text.
	
	
Risk Level 4 (46.407/50.54): (Research not otherwise approvable which presents an opportunity to understand, prevent, or alleviate a serious problem affecting the health or welfare of children.) The proposed research does not meet the criteria of the above categories but presents an opportunity to understand, prevent, or alleviate a serious problem affecting the health or welfare of children.


Provide justification for why this research of this risk level should be approved (for each group):
	

### Parental Permission (46.408/50.55)

F.	
What permission will be obtained from the parents?
 
In general, permission from both parents is required for research involving children unless one parent is deceased, unknown, incompetent, or not reasonably available, or when only one parent has legal responsibility for the care and custody of the child. However, for Categories 404/51 & 405/52, the IRB may find that the permission of one parent is sufficient. Permission from both parents should be obtained whenever possible regardless of risk level determination.

	
Permission will be obtained from both parents where possible

	
Permission from only one parent is being requested

	
A waiver of parental permission is being requested (complete IRB – Request form for Alteration or Waiver of Assent, Consent, Parental Permission found in IRBNet under Forms and Templates) This is also for the historical controls

	
A waiver of DOCUMENTATION of parental permission is being requested (complete IRB – Request form for Alteration or Waiver of Assent, Consent, Parental Permission found in IRBNet under Forms and Templates)

## Protocol Summary/Submission Application

**G. If the research is being conducted in a group setting (e.g., a classroom), in which some children have permission to participation and some do not, what is the process to ensure that those children who do not have parental permission do not participate in the research.**

N/A

**Assent (46.408/50.55)**

Adequate provisions must be made for soliciting the assent of children when in the judgment of the IRB the children are capable of providing assent and for soliciting the permission of their parents or guardians.

**H. Indicate whether the children you intend to include in the research are generally capable of providing assent taking into account the ages, maturity and psychological state of the children proposed to be involved. Please be specific:**

- All are capable
- None are capable: Explain:** The patients being studied are survivors of acute severe brain injury and would be unable to provide assent during the enrollment period when they have symptoms of PSH and are cognitively unable to provide assent.
- Some are capable: Explain:** [Click here to enter text.](#)

**I. If children are capable of providing assent, are you planning to obtain assent from the children?**

Yes  No  **N/A – none are capable**

**If YES, describe the proposed process for obtaining assent, including who will be involved and the setting and circumstances under which it will be sought:**

**If NO, a waiver of assent is being requested** (complete IRB – **Request form for Alteration or Waiver of Assent, Consent, Parental Permission** found in IRBNet under Forms and Templates).

We are requesting a Waiver of Assent (see uploaded form) for all children due to the child’s diminished cognitive functioning. Given the inclusion criteria of nature of brain injury causing subject to meet study criteria and associated sedation necessary as standard of care for these patients, we do not anticipate that any of subjects enrolled in study will be conscious enough to comprehend, process and understand the study, so we request a waiver of assent for all subjects who will be approached for study.

If child has already completed study before achieving the age of majority, we request a waiver of consent and HIPAA authorization for continued use of their data on reaching the age of majority.

A waiver of consent/ assent is also being requested for the historical controls.

**J. If assent will be obtained, describe the process and select how assent will be documented. Include in the submission package proposed assent forms or child information sheet, if any.**

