#### **Medication detail during study treatment:**

No additional maintenance medications (propranolol, bromocriptine, dantrolene, gabapentin, baclofen) will be allowed to be initiated for the first 12 hours after initiation of PENFS. Patients could continue to receive rescue medications (morphine, benzodiazepines such as lorazepam, midazolam, diazepam, clonidine) during this period for break through symptoms or remain on maintenance medications that were already in

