## Protocol Summary/Submission Application

during the initial 12 hours of use of the device; however, rescue medications will be allowed during this period. Maintenance medications would be allowed after 12 hours of device use. We will also compare the trend in scores while using the device to the trend once the device is discontinued after 120 hours of use as we will be following the trend in the CFS scores every 12 hours for an additional 72 hours after removal of the device. This will be impactful as the patient will be his/her own control. However, we recognize that this could be confounded by the initiation of maintenance medications.

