### **Aim 3a: Evaluate the change in autonomic balance with use of PENFS device**

**Methods:** We will use two separate validated modalities to evaluate the autonomic activity/balance in response to use of the device – HRV and Pupillometry. HRV denotes the beat-to-beat variability in the R-R interval on the EKG. Cardiac pacemaker automaticity is continuously altered and regulated by the autonomic nervous system (ANS). The parasympathetic system regulates HR on a beat-to-beat basis whereas the sympathetic system has slower onset but longer duration of action (16-18). Decreased HRV parameters has been shown to be associated with increased 30-day mortality in critically ill patients (19). Children with PSH were shown to have significant differences in HRV parameters compared to controls (20). We will calculate time-domain (mean heart rate, standard deviation of all average R-R intervals (SDNN), root mean square of the successive differences (RMSSD), physical stress index (PSI), approximate entropy (ApEn); successive R-R interval difference (SRD)) and frequency-domain indices (total power (TP), high frequency (HF), low frequency (LF), normalized HF, normalized LF, and LF/HF ratio) and compare the 12-hour period before and after placement of the PENFS device. Three separate 5-minute segments of continuous EKG tracings at rest (lying in bed) and body temperature 36-37.5C will be identified for both periods for comparison. Similarly, we will compare the pupillometry parameters along with direction of change before and after device placement.

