## Protocol Summary/Submission Application

complete the study. If the patient does meet CFS scoring criteria for study enrollment, we will collect the CFS score for a 12-hour period before placement of the device followed by every 12 hours while the device is in place and for an additional 72 hours after removal of the device.

**Data collection & Management:** We will collect demographics, cause of ASBI, imaging findings, sedative, pain and other neurotropic medications, and maintenance and rescue medications for PSH including their number and doses for every 24-hour period from placement of the device. We will also collect all the HRV and pupillometry parameters for the 12-hour period before and after placement of the device. For the historical cohort, we will collect demographics, cause of ASBI, imaging findings, maintenance and rescue medications used in each 24 hour period for the first 120 hours and then additional 72 hours from the time of meeting CFS score > 6 criteria. . The REDCap database for this study will be developed and managed by Quantitative Health Sciences on MCW-secure servers

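### Sedatives and analgesics given outside the PSH drug lists have no row in Table 3, so a change in background sedation across device placement could imitate or mask a PENFS effect

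*Combined protocol and SAP*

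**What the plan says.** Section 8 (Assent, item I) explains why no child is expected to be able to assent and cites the brain injury and "associated sedation necessary as standard of care for these patients". No drug is named there.

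Section E, Data collection & Management, lists for collection "sedative, pain and other neurotropic medications, and maintenance and rescue medications for PSH including their number and doses for every 24-hour period", and the sentence closes with the start point, "for every 24-hour period from placement of the device". Sedative and pain drugs are thus listed separately from the PSH drugs.

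Table 3 has one row for maintenance and one for rescue medications. Both are marked at -12 to 0 h, at 12 h, at 24 h and daily thereafter. There is no row for other sedatives or analgesics.

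The section on medication during study treatment allows "rescue medications (morphine, benzodiazepines such as lorazepam, midazolam, diazepam, clonidine) during this period" and restricts one class only: "No additional maintenance medications (propranolol, bromocriptine, dantrolene, gabapentin, baclofen) will be allowed to be initiated for the first 12 hours". Nothing is said there about background sedation.

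Aim 3a will "compare the 12-hour period before and after placement of the PENFS device" for HRV, and pupillometry likewise. The analysis entry for Hypothesis 3a is a Wilcoxon rank sum test with no covariate. Aim 2b looks at within-patient CFS change around placement and its later trend. On confounding, Aim 2b says only "we recognize that this could be confounded by the initiation of maintenance medications".

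**The concern.** There is no concurrent control group. The autonomic claim, and the first step of the CFS claim, rest on each child's 12 hours before placement against the 12 hours after. Anything else that changes at that boundary and acts on heart rate, breathing, blood pressure, tone or pupils is mixed with the device effect.

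Sedation is an obvious candidate. The protocol presents it as usual for these children, and its background section lists over-sedation and respiratory depression among the effects of the drug classes used in PSH. Respiratory rate is a CFS item. Children enter when they are symptomatic (CFS above 6) and get the device within 24 hours, a time when treatment is likely to be changing. A step-up in sedation could make an inert device look sympathoinhibitory; a wean could hide a real effect. If background sedation is not recorded in the two windows being compared, the reader of the pilot cannot tell which has happened, and the estimates carried into planning a larger trial inherit the problem.

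**Working it through.** **1. Recording windows against outcome windows.** Table 3 columns are read from the extracted text.

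| Exposure | Scheduled for -12 to 0 h? | Separate mark at 12 h? | Source |
|---|---|---|---|
| PSH maintenance drugs | Yes | Yes | Table 3 |
| PSH rescue drugs (morphine, benzodiazepines, clonidine) | Yes | Yes | Table 3; medication detail section |
| Sedatives and analgesics outside both lists | No row | No row | Table 3 |

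For the last line only the Data collection text remains, and it can be read in two ways. If the 24-hour phrase covers sedatives, recording starts at placement and hours 0-12 are merged with hours 12-24. If it covers only the PSH drugs, the timing for sedatives is not stated. Neither reading provides a record matched to the two 12-hour outcome windows.

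**2. Does the analysis deal with it elsewhere?** The Aim 3a EKG segments are standardised for rest and body temperature (36-37.5 °C), not sedation. The sensitivity analysis in the analysis overview belongs to missing data. The classification tree belongs to Hypothesis 3b, on medication use. No analysis of HRV, pupils or CFS takes sedation into account.

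**3. How large could the effect be?** The plan gives no alpha, SD, effect size or sedation figures, so there is no stated figure to reproduce. Both illustrations below set the true device effect to zero and use a two-sided 5% level. Only n = 20 comes from the protocol.

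*HRV or pupil parameter.* Simulation, 10,000 runs: before = a, with a standard normal; after = ρa + √(1-ρ²)e + d, with e standard normal, ρ = 0.3, 0.5 or 0.7, and d the sedation shift in SD units. Share of trials with p<0.05 (range over ρ):

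| Shift d | Rank sum (planned) | Signed-rank (paired) |
|---|---|---|
| 0 | 0.2-2.2% | 4.7-4.8% |
| 0.25 | 2.6-8.1% | 14.1-26.5% |
| 0.5 | 24.3-29.1% | 41.2-76.4% |
| 1.0 | 88.8-95.6% | 93.7-100% |

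*CFS.* The scale has 6 scored items of 0-3, so a maximum of 18. Assume that a step-up lowers heart rate, respiratory rate and systolic pressure by one band each, 3 points, in a net fraction f of children. Mean shift = 3f. Noncentrality of a paired t-test = (3f/SD) × √20, with an assumed SD of change of 3 or 4.

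- f = 0.20: shift 0.60; noncentrality 0.89 (SD 3) or 0.67 (SD 4); p<0.05 in 13.6% or 9.8%.
- f = 0.35: shift 1.05; noncentrality 1.57 or 1.17; 31.8% or 20.0%.
- f = 0.50: shift 1.50; noncentrality 2.24 or 1.68; 56.5% or 35.7%.

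Here f is net of weans. With 50% stepped up and 30% weaned by the same amount, f = 0.50 - 0.30 = 0.20 and the rates are 13.6% or 9.8%. With equal numbers in each direction f = 0 and the rate is 5%. The paired t-test is a convenience; the overview plans mixed models for continuous data over time.

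**The case against.** Much of the sedating exposure is already covered. Morphine, benzodiazepines and clonidine count as rescue drugs, and Table 3 records them before placement and at 12 hours. A reader might infer that sedatives are recorded only from placement and only in 24-hour bins; Table 3 contradicts that. The Section 8 remark is one clause in an assent rationale, names no drug, and does not show how much sedation falls outside the two lists. The background remark on over-sedation concerns drugs used to treat PSH, which largely overlap with those lists. All of this stands, and it narrows the gap. It does not close it: the rescue category is for breakthrough symptoms, and sedation given for other reasons has no stated place in it.

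A reader might also infer that a sedation change will be read as a device effect and can never be disentangled. The documents support neither. No such change is shown, it could go either way, and opposite changes can cancel. If the hospital chart holds time-stamped administrations, the data can be recovered; the plan itself relies on chart review for the historical cohort's medication.

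The strongest objection concerns adjustment. The protocol hypothesises that the device reduces the need for neurosedative drugs. Sedation after placement may thus be a consequence of the device, and adjusting for it, or keeping only children in whom it did not change, may remove part of a true effect or select on response. That rules out an adjusted estimate as the main result.

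Finally, this is a feasibility pilot, stated not to be powered for efficacy. That lowers the stakes, but the before/after contrasts are still stated aims.

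**Conclusion.** The point holds in a limited form. Table 3 has no row for sedatives and analgesics given outside the PSH maintenance and rescue categories, the text leaves their timing unclear, and the 12-hour before/after comparisons of HRV, pupillometry and CFS take no account of them. A change in background sedation could therefore be taken for a PENFS effect or could mask one.

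The size and direction of any such change cannot be known from the documents. On the assumed inputs, a small one-directional shift (0.25 SD) matters little under the planned rank sum test, while 0.5 SD or more would often give a nominally significant result with an inert device. Those figures assume that sedation moves the same way on average across children. This is an inexpensive improvement to what the pilot can support, not a flaw that invalidates it.

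**What to change.** - Reconcile the Data collection text with Table 3. Add a row for all background sedatives and analgesics (infusion rates and bolus doses), taken time-stamped from the medication administration record, for -12 to 0 h and 0 to 12 h separately. Time stamps also allow alignment with the EKG segments and pupil readings.
- Report each child's change in background sedation beside that child's changes in HRV, pupillometry and CFS.
- Name sedation next to maintenance drugs as a confounder in Aim 2b.
- Keep the unadjusted within-child change as the main result. Add one sensitivity analysis, labelled exploratory, either in children whose background sedation was unchanged from -12 to +12 h or adjusted for sedation change.

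This concerns recording and reporting only; clinical care is unchanged. The cost is some extra abstraction for about 20 children. The unchanged-sedation subset may be small. Because the sensitivity analysis conditions on something the device may itself affect, it may understate a true effect, and the report should say so.

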**Describe the process:**

- All minors will sign the assent signature line on the parental permission form. Minors >12 years of age will be asked to sign the assent signature line on the parental permission form.
- All minors will sign a separate assent form
- Minors in the age range of seven to twelve years of age will sign a separate assent form

## Protocol Summary/Submission Application

Verbal assent will be obtained and discussion documented in research records

**K. Describe the plan for obtaining legally effective informed consent and HIPAA Authorization at the age of majority [18] or describe why it is not applicable** (review **Guidance – Consent for Continued Participation When a Child Reaches Age 18** found in IRBNet under Forms and Templates):

Age of Majority Plan:

If a subject is in PICU and reaches the age of majority, we will assess already enrolled subject for their consent capacity during the time when device is already on the subject (active study participation phase). We do not anticipate the child will be conscious enough in this period and so, re-consent will be obtained from parent or legal guardian if subject is still in PICU. If the device has already been removed from the subject and the only study participation pertains to use of already collected data, we request a waiver of re-approach, consent and HIPAA authorization for continued use of data at the age of majority.

If the subject has already left PICU and there is no active study participation, no follow up contact will be made to subject or family as they are lost to follow up. The only study activity ongoing is continued use of their collected research data and we request waiver of consent and HIPAA authorization for continued use of this data, for the reason subject is lost to follow up.

**Contact the CW HRPP office to obtain appropriate supplements if you intend to enroll other vulnerable populations such as pregnant women, fetuses and neonates, prisoners (including incarcerated minors), or cognitively impaired adults.**

